Amyloidopathy, Cholinopathy, Dopamine Responsiveness and Freezing of Gait in PD

NCT03647137

05/31/2022

Statistical Analysis Plan

In this proposal, the investigators present data suggesting that L-DOPA refractory freezing of gait (FoG) is associated with comorbid cholinopathy and amyloidopathy in Parkinson's disease.

The investigators propose to test the novel **hypothesis** that comorbid amyloidopathy may be a possible mechanistic factor underlying the poor response of FoG to dopaminergic therapy in advancing PD. In contrast, isolated cholinopathy (without amyloidopathy) would be expected to be associated with preserved dopamine responsiveness of FoG.

For this purpose, the investigators propose to perform detailed motor, including FoG, testing in PD patients "on" and "off" their dopaminergic medications and relate this to dopaminergic 11C- DTBZ, vesicular acetylcholine transporter 18F-FEOBV and amyloid 11C-PIB brain PET imaging in PD subjects with and without FoG.

Our statistical approach is to run a series of hierarchical ordinal logistic regression models, predicting freezing type (L-DOPA responsive, diminished L-DOPA responsiveness, and L-DOPA non-responsive) from dopaminergic (DTBZ), cholinergic (FEOVB), and amyloid (PIB) PET distribution volume ratio (DVR) of the striatum. The null model includes in it striatal DTBZ only. The FEOVB model adds a term for striatal cholinergic innervation. The interaction model, that most directly tests our comorbidity hypothesis adds an interaction term between FEOVB and PIB PET. Goodness of fit for the FEOVB model is compared against the null model, and the interaction model is compared against the FEOVB model.

Furthermore, based on recent clinical observations that serotonergic drugs, like the popular anti-depressant SSRI drugs, are associated with significantly lower build-up of beta-amyloid plaques in the elderly population, and based on the investigators' subsequent observation of an intriguing inverse relationship between -amyloid plaque deposition and striatal serotonergic terminal in PD, the investigators propose to perform an exploratory sub-study to test an exploratory hypothesis that PD subjects with FoG will exhibit not only higher striatal -amyloid but also lower striatal serotonergic innervation (as determined by 11C-DASB serotonin PET imaging) compared to PD subjects without FoG. Due to a large number of participants taking anti-depressant drugs the number of participants with additional 11C-DASB PET scans was too small to perform a statistical analysis

Protocol Synopsis

Freezing of gait (FoG) becomes more prevalent in advanced Parkinson's disease (PD) and afflicts approximately half of all patients with PD. With disease progression, FoG usually becomes a major contributor to loss of mobility, falls, and decreased quality of life. Elucidation of possible mechanisms underlying dopamine non-responsiveness of gait disturbances in PD, therefore, has high clinical importance.

The premise of this project is that our preliminary data show that 'uncomplicated' PD—when still in a stage of predominant nigrostriatal dopaminergic denervation—does not have to be a very disabling disease *per se*. As a matter of fact, we found that gait speed in patients with predominant nigrostriatal degeneration is not significantly slower from healthy non-PD control subjects. However, our preliminary data show also that the emergence of non-dopaminergic extra-nigral pathologies in PD may result in significant disability due to FoG. If the association of amyloidopathy and dopamine refractoriness of FoG can be confirmed then this would provide a window for targeted interventions as these at risk-individuals could receive anti-amyloid targeted therapies that might prevent or improve disability in PD. A particular advantage of PD is that the low but symptomatic level of amyloidopathy provides a unique window of opportunity to intervene relatively early in the amyloid cascade. Serotonergic drugs that are already on the market may deserve further study as potential novel anti-amyloid investigational therapeutics, especially when administered very early in the disease course and well before the development of motor complications in PD. Such early and targeted anti-amyloid investigational therapy will critically depend on appropriate biomarker identification of subjects who are at risk of β -amyloid deposition.

The overarching goal of this study is to investigate the relationship between FoG and extranigral pathologies in PD and to test the hypothesis that comorbid amyloidopathy is a mechanistic factor underlying the poor response of FoG to dopaminergic therapy in advancing PD whereas FoG in cholinopathy alone is associated with preserved dopamine responsiveness. To achieve the goals of this project, patients with PD with and without FoG will undergo detailed FoG and gait motor testing in PD patients "on" and "off" their dopaminergic medication. Findings will be related to β -amyloid 11C-PIB, vesicular acetylcholine transporter 18FFEBBV, VMAT2 11C-DTBZ and, in a subset, SERT 11C-DASB brain PET imaging data. Interested subjects may also participate in an additional biomechanical/EMG of FoG and ocular function studies, to be performed on another day.

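### The interaction step is compared with a model that has no PIB term, so PIB alone can pass as comorbidity, and neither fit comparison addresses isolated cholinopathy

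*Combined protocol and SAP*

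**What the plan says.** The Statistical Analysis Plan section gives the first half of the hypothesis as "comorbid amyloidopathy may be a possible mechanistic factor underlying the poor response of FoG to dopaminergic therapy in advancing PD" and sets against it that "isolated cholinopathy (without amyloidopathy) would be expected to be associated with preserved dopamine responsiveness of FoG". The Protocol Synopsis repeats the second half in its overarching goal: "FoG in cholinopathy alone is associated with preserved dopamine responsiveness".

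The outcome is a three-level ordinal freezing type, running from L-DOPA responsive to non-responsive. The predictors listed are dopaminergic (DTBZ), "cholinergic (FEOVB), and amyloid (PIB) PET distribution volume ratio (DVR) of the striatum". (The model description spells the FEOBV tracer FEOVB.) Three models are described:

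- null: DTBZ;
- FEOBV model: DTBZ + FEOBV;
- interaction model, which "adds an interaction term between FEOVB and PIB PET".

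The inference consists of two comparisons: "Goodness of fit for the FEOVB model is compared against the null model", and "the interaction model is compared against the FEOVB model". The SAP singles out the interaction model as the most direct test of comorbidity. It does not name a fit criterion, a significance level, a centring rule or a sample size. PIB is in the predictor list, but no step is described as adding it as a main effect.

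**The concern.** A comparison of nested models tests whatever terms differ between them. For the second comparison to test comorbidity, the only difference should be the FEOBV-by-PIB interaction. As described, the smaller model has no PIB at all, so the comparison also picks up any plain association between PIB and response. An amyloid effect that is the same at every level of cholinergic innervation could then be reported as evidence that the combination matters.

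Separately, the second half of the hypothesis concerns how well freezing responds when cholinergic loss is present and amyloid is not. Neither comparison looks there. The Protocol Synopsis links confirmation to anti-amyloid treatment of at-risk patients, so it matters which of these statements the data support.

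**Working it through.** The documents give no sample size, effect size, significance level or DVR distribution, so there is no planned figure to reproduce. The check compares the terms in each model and then illustrates the size by simulation with assumed inputs.

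**1. What the second comparison tests.** The comparator is DTBZ + FEOBV. There are two readings of the interaction model.

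- *PIB main effect included.* The models differ by PIB and FEOBV×PIB. The comparison is a joint 2-df test that a PIB main effect alone can pass.
- *PIB main effect left out.* The models differ by the product only. Write FEOBV = m + s·zF and PIB = M + S·zP, with zF and zP standardised. Then FEOBV×PIB = mM + sM·zF + mS·zP + sS·zF·zP. The first two terms are absorbed by the intercepts and FEOBV. What remains is sS·(r·zP + zF·zP), with r = m/s. For independent tracers, PIB itself makes up r²/(r²+1) of that variance:
  - r = 3: 9/10 = 90%
  - r = 5: 25/26 = 96%
  - r = 8: 64/65 = 98%

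So the uncentred product is nearly PIB. With both tracers mean-centred, r = 0 and the share is 0.

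**2. Size when PIB acts alone.** Assumptions: proportional-odds data, 5% likelihood-ratio test, no interaction, PIB log-OR 0.8 per SD. Two separate sets of simulations gave these percentages of significant studies at N = 40/60/80:

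| Comparison | Set A | Set B |
|---|---|---|
| Uncentred product only, vs FEOBV | 66-69 / 81-84 / 91-93 | 60 / 78 / 92 |
| PIB + product, vs FEOBV (2 df) | 60 / 78 / 88 | 54 / 74 / 86 |
| PIB in both models (1 df) | 7 / 7 / 6 | 6-8 |

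Set A also assumed a DTBZ-deficit log-OR of 0.5, a FEOBV-deficit log-OR of 0.6, a 50/25/25 outcome split and r from 3 to 8, with 1,000 studies per cell. Centred tracers with no PIB main effect gave 8-9% there.

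A third set used N = 30/60/100, FEOBV mean 1.0 and SD 0.15, and PIB mean 1.1 and SD 0.12 (all assumed):

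- PIB log-OR 0.5: 31/53/74% (product only) and 28/45/65% (2 df).
- PIB log-OR 1.0: 75/97/99.8% and 68/94/99%.
- With PIB in both models, for either PIB effect: 9.0-9.8% at N = 30, falling to about 6.6% at N = 100. This is small-sample inflation of the likelihood-ratio test.
- Centred product, no PIB main effect: 5.9-8.5%.

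**3. The isolated-cholinopathy half.** FEOBV versus null contains no PIB, so it yields one slope pooled over amyloid. A gain in fit at the next step says that PIB-containing terms help, not what the response is at low FEOBV and low PIB. In the third set at N = 100, a zero FEOBV slope at 1 SD below mean PIB (with an interaction) made the two comparisons significant in 91% and 89% of studies (2-df version of the second). A slope of 0.8 at every PIB level plus a PIB effect, with no interaction, gave 96% and 95%. Two different states at low PIB produce the same pair of positive results.

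**The case against.** **PIB may be in the model.** It is in the predictor list, and a hierarchical approach may imply main effects. A reader might infer that the plan definitely omits PIB; the documents leave that open. But putting PIB into the interaction model alone does not cure the comparison, because the stated comparator still lacks it.

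**A PIB main effect is partly what the study seeks.** The Protocol Synopsis speaks of confirming an association between amyloidopathy and refractory freezing, and an additive PIB effect would support that. It would also make freezers with cholinergic loss and low amyloid more responsive than those with both pathologies. This stands: a PIB-only result is not spurious. It is an amyloid association, though, and does not show the FEOBV-by-PIB interaction on which the SAP rests comorbidity.

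**Direction will be visible.** A reader might infer that an interaction of the wrong sign would be accepted because only fit is compared. The documents do not support that: the SAP states the direction in words, a fitted model gives signed coefficients, and nothing says they will go unread.

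**The rates are assumed.** This also stands. They depend on the PIB effect, N and coding, and centred tracers without a PIB main effect largely remove the problem. The SAP states no centring, so the conclusion would turn on an unstated choice.

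**A stricter demand is tempting for the second half:** that preservation be judged by a margin on the FEOBV slope at low PIB, with a steep slope counted as loss of response. The documents speak of the level of responsiveness, not a slope, and the two can disagree. In assumed examples, a zero low-PIB slope with a 15/35/50 outcome split gave a true probability of response of 0.12 at low FEOBV and low PIB. A slope of 1.2 with PIB log-OR 0.8 and a 70/15/15 split gave 0.69. A slope rule could therefore certify preservation where response is rare and withhold it where response is common.

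**Conclusion.** The comparator point holds. Followed as written, the interaction step does not isolate the interaction, and PIB alone can be read as comorbidity with cholinopathy. With PIB log-OR 0.8 per SD and N = 40 to 80, about 55-93% of studies with no interaction are significant there, against about 6-8% with PIB in both models. These are illustrations, not estimates for this study. The structural point, that the comparator contains no PIB, comes from the text and needs no assumption.

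The second point holds in limited form: neither fit comparison by itself addresses preserved response in cholinopathy without amyloidopathy. That does not mean the fitted model could not address it, only that the plan does not state the estimate that would. Nor does it follow that any reported association with amyloid is wrong.

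**What to change.** - Add a DTBZ + FEOBV + PIB model. Compare it with the FEOBV model and report that step separately, as an amyloid association.
- Fit DTBZ + FEOBV + PIB + FEOBV×PIB and compare it with the three-term model by a 1-df likelihood-ratio test.
- Base the comorbidity claim on the signed interaction coefficient from the four-term model with its 95% CI. The hypothesised sign is negative if the outcome is ordered towards non-responsive and both tracers enter as DVR.
- For isolated cholinopathy, report descriptively, with 95% CIs, the predicted probability of the L-DOPA-responsive category at low FEOBV/low PIB and at low FEOBV/high PIB, at stated tracer values and mean DTBZ.
- Do not read a non-significant FEOBV slope, or the FEOBV-versus-null comparison, as evidence of preservation.

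The SAP reports in the past tense that "the number of participants with additional 11C-DASB PET scans was too small to perform a statistical analysis", so some data already existed when this text was written. Tracer values chosen after the data were seen should be labelled post hoc.

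The cost is one extra model term, a changed comparator and a few reported estimates, with no new data. The low-PIB estimates may be imprecise. At the 10th percentiles of both tracers, under assumed inputs (normal PIB, 50/25/25 split, zero low-PIB slope), the median 95% interval for the predicted probability was 0.15-0.84, 0.20-0.79 and 0.23-0.76 at N = 40, 60 and 80. That width should be shown, since it limits what can be said about preservation.

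### Striatal DTBZ is adjusted only as a main effect, so part of any DTBZ × PIB effect may be misattributed to FEOBV × PIB if the two tracers are correlated

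*Combined protocol and SAP*

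**What the plan says.** All the modelling is described in one paragraph under Statistical Analysis Plan. The investigators will "run a series of hierarchical ordinal logistic regression models, predicting freezing type (L-DOPA responsive, diminished L-DOPA responsiveness, and L-DOPA non-responsive"), using striatal DVRs of three tracers. The sequence is:

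- Null model: "The null model includes in it striatal DTBZ only".
- Second model: "The FEOVB model adds a term for striatal cholinergic innervation".
- Third model: it "adds an interaction term between FEOVB and PIB PET".

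FEOVB in that paragraph is the tracer called FEOBV elsewhere. For the decisive step, "the interaction model is compared against the FEOVB model", and the third model is singled out: "The interaction model, that most directly tests our comorbidity hypothesis".

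The Protocol Synopsis states the specificity that this step must support. Comorbid amyloid goes with a poor drug response, whereas "FoG in cholinopathy alone is associated with preserved dopamine responsiveness".

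The documents describe no DTBZ × PIB term, rival interaction or sensitivity model. They also give no sample size, significance level, test statistic or tracer correlation, and they do not say whether a PIB main effect enters with the product.

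**The concern.** Having DTBZ in every model keeps the FEOBV main effect from simply reflecting dopaminergic loss. It does not do the same for FEOBV × PIB. Where two predictors are correlated, the product of one with a third variable is correlated with the product of the other, and a main effect does not remove that.

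DTBZ and FEOBV are both measured in the striatum, so some correlation is plausible. The outcome is the response to a dopaminergic drug, so an amyloid effect that varies with dopaminergic denervation is a reasonable rival explanation, although the documents do not propose it.

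What is at stake is attribution. The study's thesis is that cholinopathy together with amyloidopathy marks refractory freezing. A significant third step, as planned, cannot be told apart from amyloid acting together with nigrostriatal loss.

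**Working it through.** **Inputs.** The three-level ordinal outcome, the three nested models and the striatal region come from the Statistical Analysis Plan. The plan has no power or sample-size figure to reproduce. Everything else is assumed: a 5% level, N = 45 and 60 (with 40, 80 and 150 as checks), DTBZ–FEOBV correlation ρ from 0 to 0.7, and the size of the rival effect in log-odds per SD × SD.

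**Step 1: how much leaks.** Let D, F and P be standardised, jointly normal DTBZ, FEOBV and PIB, with P independent of D and F.

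- Cov(D·P, D) = E[D²P] = 0, so the DTBZ main effect absorbs none of D·P.
- Cov(D·P, F·P) = E[D·F]·E[P²] = ρ, and Var(F·P) = 1.
- If D·P is omitted and its coefficient is b, the F·P coefficient therefore picks up about ρ × b on the linear predictor scale. A logistic fit will shrink this somewhat.

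| ρ | b = −0.9 | b = −0.45 |
|---|---|---|
| 0.3 | −0.27 | −0.135 |
| 0.5 | −0.45 | −0.225 |
| 0.7 | −0.63 | −0.315 |

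**Step 2: how often that is significant.** Proportional-odds data were simulated with a DTBZ × PIB effect and no FEOBV × PIB effect, and tested by a 1-df likelihood-ratio test at 5%. Entries are the percentage of studies that falsely detect FEOBV × PIB, at ρ = 0.3 / 0.5 / 0.7.

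| Setting | N | Rival effect (absolute) | FEOBV × PIB tested without DTBZ × PIB | DTBZ × PIB in both models |
|---|---|---|---|---|
| Main run | 45 | 0.9 | 14 / 22 / 36 | 6–10 |
| Main run | 60 | 0.9 | 12 / 27 / 44 | 6–10 |
| Repeat, 1,500 studies per cell | 45 | 0.9 | 15 / 26 / 41 | 7–9 |
| Repeat, 1,500 studies per cell | 60 | 0.9 | 15 / 30 / 51 | 7–9 |
| Moderate rival, 400 studies per cell | 45 | 0.45 | 11 / 13 / 14 | not run |
| Check, 1,000 studies per cell | 40 | 0.5 | 8 / 13 / 20 | 7–8 |
| Check, 1,000 studies per cell | 40 | 1.0 | 14 / 26 / 45 | 8 |

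The repeat took PIB to correlate −0.1 with DTBZ and −0.2 with FEOBV. The 1,000-study check took PIB as independent of both.

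- With no rival effect, the 1-df test rejects in about 4–7% at N = 45 and 7–10% at N = 40. Most of the residual 6–10% in the last column is thus ordinary small-sample inflation of this test.
- At ρ = 0 there is almost no leak: a rival of 1.0 gives 10% / 9% / 8% at N = 40 / 80 / 150.
- The leak grows with sample size: at ρ = 0.5 and a rival of 1.0 it is 26% / 42% / 66% at N = 40 / 80 / 150.
- The result does not hang on how PIB enters. In a further run of 600 studies per cell (rival 0.9, N = 45), entering the product without a PIB main effect gave 14 / 24 / 40. Entering PIB and the product together on 2 df gave 14 / 21 / 35.

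**Step 3: cost of the extra term.** Corr(D·P, F·P) = ρ, so adding D·P inflates the variance of the F·P estimate by about 1/(1 − ρ²). That is 1/0.91 = 1.10, 1/0.75 = 1.33 and 1/0.51 = 1.96. With a true FEOBV × PIB effect of −0.9 at N = 45, simulated power changed as follows.

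| ρ | First run (1,500 studies) | Second run (600 studies) |
|---|---|---|
| 0.3 | 73% to 70% (−3) | 76% to 71% (−5) |
| 0.5 | 74% to 64% (−10) | 70% to 61% (−9) |
| 0.7 | 72% to 49% (−23) | 73% to 49% (−24) |

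**The case against.** The strongest reply is that the problem needs two facts the documents do not supply: an amyloid effect that depends on nigrostriatal loss, and correlated tracers. The Protocol Synopsis leans the other way. It treats predominantly nigrostriatal disease as not very disabling and places the disability in non-dopaminergic pathology. The −0.9 rival is also as strong as the effect assumed for the study's own hypothesis in the power check, and at half that size the excess over the test's ordinary error rate is modest. All of this stands, and it limits the point to a conditional one.

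A reader might infer that an amyloid-by-dopamine effect will be reported as comorbidity. The documents do not support that. Even under the strong rival at N = 45 to 60, the 1-df test is non-significant in about half or more of the simulated studies. A reader might also infer that the error must favour the hypothesis. That follows from the sign chosen for the rival and a positive correlation, not from the plan.

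It can also be said that the missing PIB main effect is the more direct gap. If PIB and the product enter together, a plain PIB effect of 0.6 log-odds per SD with no interaction makes the 2-df step significant in 41% / 71% / 93% of studies at N = 40 / 80 / 150. That is a separate issue. Resolving it does not settle this one, because the main results above already have PIB in both models.

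**Conclusion.** The point holds in conditional form. As planned, a significant FEOBV × PIB step cannot separate cholinergic-amyloid comorbidity from amyloid combined with nigrostriatal loss.

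For N = 45 to 60 and ρ = 0.3 to 0.7, false detection on 1 df is about 12–44% for a strong rival (a repeat with other settings reached 51%) and about 8–20% for a moderate one. It is about 6–10% with DTBZ × PIB in both models. The sample size, correlation and rival effect are all assumptions. With no rival effect or uncorrelated tracers the issue largely disappears.

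Nothing here shows that the rival effect exists or that a positive result would be wrong. The planned comparison need not be replaced. A specificity check is worth adding because the study's central claim is one of specificity and the check uses data already held.

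**What to change.** Keep the planned comparison and add one specificity analysis:

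- Compare {DTBZ, FEOBV, PIB, DTBZ × PIB} with the same model plus FEOBV × PIB, stating explicitly that the PIB main effect is in both.
- Report the likelihood-ratio test, both interaction estimates with 95% CIs, and the striatal DTBZ–FEOBV correlation.
- Describe the effect as specific to cholinopathy only if the adjusted FEOBV × PIB interval excludes zero. Otherwise state that the data do not separate the cholinergic from the dopaminergic interaction. Failure to exclude zero is not evidence for the dopaminergic reading, or for striatal denervation in general.

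A rule that the adjusted estimate should keep its sign and most of its size would not do. With the strong rival at N = 45, 44–78% of false positives keep their sign and over half their size after adjustment.

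The work is one extra nested comparison. The price is precision: at N = 45, roughly 5 points of power at correlation 0.3 and about 23 at 0.7. It should therefore remain a sensitivity analysis. If the main result is already known when it is added, it should be labelled post hoc.

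### The comorbidity hypothesis has a direction, but the only assessment named for it is a model-fit comparison that ignores sign and has no PIB term in the comparator

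*Combined protocol and SAP*

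**What the plan says.** The Statistical Analysis Plan gives the hypothesis in two halves. The first is that "comorbid amyloidopathy may be a possible mechanistic factor underlying the poor response of FoG to dopaminergic therapy in advancing PD". The second is that "isolated cholinopathy (without amyloidopathy) would be expected to be associated with preserved dopamine responsiveness of FoG". The Protocol Synopsis repeats both.

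The outcome is a three-level freezing type, ordered from responsive to non-responsive, modelled by ordinal logistic regression. The models are built in steps:

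- The null model holds striatal DTBZ only.
- "The FEOVB model adds a term for striatal cholinergic innervation" (the plan's spelling of FEOBV).
- "The interaction model, that most directly tests our comorbidity hypothesis adds an interaction term between FEOVB and PIB PET".

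The assessment is then one sentence: "Goodness of fit for the FEOVB model is compared against the null model, and the interaction model is compared against the FEOVB model".

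No PIB main effect is mentioned. Nor are the fit statistic, an alpha level, an expected sign, a coefficient or odds ratio to be reported, a confidence interval, or a rule for what would count as support. No sample size is given.

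**The concern.** The hypothesis says which combination of pathologies is harmful, whereas the named comparison asks only whether adding amyloid terms improves fit. Three different truths can produce that improvement: the hypothesised interaction, the opposite interaction, and an amyloid effect that does not depend on cholinergic status at all.

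The sign is easy to misread. FEOBV enters as innervation, so a high value is healthy, while a high PIB value is pathological. With a PIB main effect in the model and the outcome coded toward non-response, the hypothesis implies a negative product coefficient. A positive one may look like 'both together matter', but it means the amyloid effect is larger where innervation is preserved.

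The Protocol Synopsis says that confirmation would point to patients who might be offered anti-amyloid treatment. An interaction read the wrong way round would point to the wrong subgroup. With no planned interval, a null comparison would not show which effects remain possible.

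**Working it through.** The plan states no sample size, power or alpha, so there is no figure of its own to reproduce.

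**1. Sign-blindness (exact).** Write the log-odds of a worse freezing type as η = b1·DTBZ + b2·FEOBV + b3·PIB + b4·FEOBV×PIB. Replacing PIB by −PIB reverses the signs of b3 and b4 and leaves the maximised likelihood unchanged. A likelihood-ratio or AIC comparison therefore carries no information on direction.

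**2. What direction means.** With FEOBV and PIB standardised, the log odds ratio per SD of PIB at FEOBV value z is b3 + b4·z. Take b3 = +0.8 (assumed):
- b4 = −0.8: at z = −1 it is 0.8 + 0.8 = 1.6 (odds ratio 4.95); at z = +1 it is 0 (odds ratio 1). This is the hypothesis.
- b4 = +0.8: at z = −1 it is 0 (odds ratio 1); at z = +1 it is 1.6 (odds ratio 4.95). This is the reverse.

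With b3 = 0 and b4 = +0.8, the value at z = −1 is −0.8 (odds ratio 0.45), so amyloid looks protective at low FEOBV. The opposite interaction can thus take more than one form.

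**3. Simulation.** All inputs are assumptions: independent standardised predictors, DTBZ −0.3, FEOBV −0.7, three outcome levels of roughly similar size, 5% level, 300 replicates, Monte Carlo error up to √(0.5×0.5/300) ≈ 3 points. The reduced model is DTBZ + FEOBV. The full model adds PIB and the product (2 df). The 1-df column has PIB in both models.

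| True amyloid effect | N | 2 df | AIC | 1 df |
|---|---|---|---|---|
| Interaction −0.8 (hypothesised) | 40 | 54% | 72% | 61% |
| Interaction +0.8 (opposite) | 40 | 56% | 74% | 63% |
| Interaction −0.8 (hypothesised) | 80 | 83% | 91% | 87% |
| Interaction +0.8 (opposite) | 80 | 80% | 92% | 88% |
| PIB main effect 0.8 only | 40 | 62% | 81% | 6% |
| PIB main effect 0.8 only | 80 | 91% | 96% | 8% |

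Under the opposite truth, every winning fit had the contradicting sign.

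**4. A sign check alone is not enough.** Under a pure PIB main effect, the share of studies that win on 2 df and also show a negative coefficient is 62.3% × (1 − 0.513) = 30% at N=40 and 90.7% × (1 − 0.493) = 46% at N=80. With PIB in both models it is 6.3% × (1 − 0.474) = 3% and 7.7% × (1 − 0.435) = 4%.

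**5. Product without a PIB term.** If only the product is added, the PIB slope is b4·FEOBV. DVRs are positive, so a positive b4 makes amyloid harmful everywhere but least harmful at low FEOBV: at 30% lower FEOBV the slope is 0.7·b4. A negative b4 makes amyloid protective everywhere. Neither represents the hypothesis. In a check at assumed N=45 with PIB +0.8, this model won in 44% of studies when the true interaction was −0.8 and in 79% when it was +0.8. Every winning coefficient was positive under both truths.

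**6. After the fix.** At N=45 with PIB +0.8 and PIB in both models, the 1-df wins had a negative coefficient in 100% of cases under the hypothesised truth and 0% under the opposite. The direction rule costs almost no power: on the 2-df test of step 3, wins under −0.8 go from 54.3% to 54.0% at N=40 and stay at 83.3% at N=80.

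**The case against.** A reader might infer that the plan would declare an opposite interaction to be support. The documents do not say so. They say that fit is compared, they state the direction of the hypothesis in words, and a fitted ordinal model yields signed coefficients that an analyst can read against it. What stands is narrower: fit is the only criterion named for the model said to test the hypothesis, and nothing commits the analyst to checking direction.

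It is also fair to say that every likelihood-ratio test or AIC comparison is sign-blind, so the near-equal percentages restate a symmetry. They are illustrations under assumed inputs. Likewise, with no amyloid effect about half of the significant results point the wrong way, but that is half of roughly 5% of studies and should not be quoted without that denominator.

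The strongest objection is that stating an expected negative sign, with no other change, would do harm. In the product-only model of step 5, a result generated by the hypothesis gives a positive coefficient and would be labelled a contradiction. This is right, and it makes the PIB main effect a condition of any sign rule. The missing PIB term is arguably the larger of the two gaps. Adding it does not remove the sign problem, as the 1-df column shows (61% against 63%, 87% against 88%).

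**Conclusion.** The concern holds in this form: the named comparison cannot distinguish the hypothesised interaction from its opposite, and because the comparator omits PIB it cannot distinguish either from an amyloid main effect. If the product enters without PIB, its sign has no usable interpretation.

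The sign-blindness and the product-only algebra need no assumption about sample size. The percentages do: N, effect sizes, predictor distributions and the 5% level are all assumed, and they show only that the ambiguity is not a rare event when effects are sizeable. The documents do not support the claim that a contradicting result will be reported as confirmation. They support the claim that the plan contains nothing to prevent it. This should be corrected, because the change is small and bears on the study's central claim.

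**What to change.** Amend the model description in the Statistical Analysis Plan as follows.

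1. Include the PIB main effect in both compared models, so that the interaction is tested on 1 df. Centre or standardise FEOBV and PIB.
2. State that, with the outcome coded toward non-response and FEOBV coded as innervation, the hypothesised product coefficient is negative. Alternatively, code FEOBV as a deficit and state the reversed sign.
3. Report the odds ratio per SD of PIB for a worse freezing type at low and at high FEOBV (for example the 25th and 75th percentiles), and their ratio, each with a 95% CI.
4. Treat the hypothesis as supported only if the interaction improves fit and the PIB effect is harmful and larger at low FEOBV. Report an opposite sign as contradicting the hypothesis. Interpret a null result from the confidence interval.

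The cost is SAP wording, one additional model term and a few derived estimates. No new data are needed.
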